Overall Rationale for the Amendment:

The primary purpose of this amendment is to align the visit schedule nomenclature with other CITADEL protocols.

This amendment includes the changes to the Protocol INCB 50465-203 (01 MAR 2017) summarized below. A redline version of the amendment depicting the updated and previous text is also provided.

1. **Synopsis; Section 6, Study Assessments (Tables 6 and 7); Section 7.5.4, Electrocardiograms; Section 7.7.1, Blood Sample Collection (Table 9); Section 7.9.1, Distribution of Subject Reminder Cards**

Description of change: The study visits were changed to Weeks 4, 8, 12, etc (instead of Day 1 of Week 5, 9, 13, etc). A similar change was made to the 12-week visit schedule. Only the names of the visits were changed, the timing of the visits remained the same.

Rationale for change: To align this study with future CITADEL studies, many of which will be conducted at the same sites.

2. **Section 4.5, Overall Study Duration; Section 6.5, End of Study**

Description of change: Clarified the timing of end of study and that subjects receiving study treatment at the time of the final analysis will continue to receive study treatment until withdrawal criteria are met.

Rationale for change: Clarification.

3. **Section 6, Study Assessments (Tables 6 and 7); [REDACTED] Section 7.5.6.1, Chemistry and Hematology**

Description of change: Added a line for *Pneumocystis jiroveci* pneumonia (PJP) prophylaxis; added collections for serum chemistry, hematology, and serology; and made minor corrections. [REDACTED]

Rationale for change: To ensure PJP prophylaxis is appropriately administered and blood samples are taken as required.

4. **Section 5.2.1.2, Supply, Packaging, and Labeling; Section 5.2.2.2, Supply, Packaging, and Labeling**

Description of change: Replaced text describing how PJP prophylactic drugs will be procured by site.

Rationale for change: To provide additional details about how PJP prophylactic drugs will be procured.

5. **Synopsis; Section 3.2, Subject Exclusion Criteria**

Description of change: Modified the HBV and HCV exclusion criteria.

Rationale for change: Based on emerging data from INCB 50465-101, INCB050465 does not appear to cause liver toxicity. The HBV and HCV exclusion criteria have been made consistent with criteria used for other PI3K inhibitors, which generally allows enrollment of subjects that have been infected with HBV or HCV, but excludes subjects with an active infection based on DNA or RNA tests, respectively.

6. **Incorporation of administrative changes.** Other minor, administrative changes have been incorporated throughout the Protocol and are noted in the redline version of the amendment.

# LIST OF ABBREVIATIONS

Abbreviation	Term
AE	adverse event
ALT	alanine aminotransferase
AST	aspartate aminotransferase
BMI	body mass index
bpm	beats per minute
CI	confidence interval
CMV	cytomegalovirus
CR	complete response
CRF	case report form
CRR	complete response rate
CT	computed tomography
CTCAE	common terminology criteria for adverse events
DOR	duration of response
ECG	electrocardiogram
ECOG	Eastern Cooperative Oncology Group
EWB	emotional well-being
FAS	full analysis set
FDA	Food and Drug Administration
FL	follicular lymphoma
FLIPI	Follicular Lymphoma International Prognostic Index
FWB	functional well-being
IDMC	independent Data Monitoring Committee
IRC	Independent Review Committee
LYMS	lymphoma subscale
MedDRA	Medical Dictionary for Regulatory Activities
MRI	magnetic resonance imaging
NCI	National Cancer Institute
NE	not evaluable
1	non-Hodgkin lymphoma

Abbreviation	Term
ORR	objective response rate
OS	overall survival
PD	progressive disease
PFS	progression-free survival
PJP	Pneumocystis jirovecii pneumonia
	С
PP	per protocol (population)
PR	partial response
PT	preferred term
PWB	physical well-being
QD	once daily
QTcB	QT interval corrected using Bazett's formula
QTcF	QT interval corrected using Fridericia's formula
SAP	Statistical Analysis Plan
SD	stable disease
SOC	system organ class
SWB	social/family well-being
TEAE	treatment-emergent adverse event
ULN	upper limit of normal
WHO	World Health Organization

#### 1. INTRODUCTION

This is a Phase 2, multicenter, open-label study designed to evaluate the efficacy and safety of 2 INCB050465 treatment regimens in participants with relapsed or refractory FL who have received at least 2 prior systemic therapies.

Section 1 of the Protocol provides a detailed description of the investigational product, target patient population, rationale for doses to be examined, and potential risks and benefits of treatment with INCB050465.

The purpose of this SAP is to provide details of the statistical analyses that have been outlined in the study INCB 50465-203 Protocol. The scope of this plan includes the interim and final analyses that are planned and will be executed by the Department of Biostatistics or designee,

# 2. STUDY INFORMATION, OBJECTIVES, AND ENDPOINTS

# 2.1. Protocol and Case Report Form Version

This SAP is based on INCB 50465-203 Protocol Amendment 9 dated 23 DEC 2019 and CRFs approved 13 NOV 2018. Unless superseded by an amendment, this SAP will be effective for all subsequent Protocol amendments and CRF versions.

# 2.2. Study Objectives and Endpoints

Table 1 presents the objectives and endpoints.

**Table 1:** Objectives and Endpoints

Objectives	Endpoints
Primary	
To assess the efficacy of INCB050465 in terms of ORR in participants with relapsed or refractory FL.	ORR defined as the percentage of participants with a CR or PR as defined by revised response criteria for lymphomas (Cheson et al 2014), as determined by an IRC.
Secondary	
To assess CRR.	CRR defined as the percentage of participants with a CR as defined by revised response criteria for lymphomas (Cheson et al 2014), as determined by an IRC.
To assess DOR.	DOR defined as the time from first documented evidence of CR or PR until disease progression or death from any cause among participants who achieve an objective response (ie, CR or PR), as determined by radiographic disease assessment provided by an IRC.
To assess PFS.	PFS defined as the time from the date of the first dose of study treatment until the earliest date of disease progression, as determined by radiographic disease assessment provided by an IRC, or death from any cause.
To assess OS.	OS defined as the time from the date of the first dose of study treatment until death from any cause.
To assess best percentage change in target lesion size.	Best percentage change in target lesion size from baseline, where target lesion size is measured by the sum of the product of the diameters of all target lesion sizes.
To characterize the safety and tolerability of INCB050465.	Safety measured by clinical assessments, including vital signs and physical examinations, 12-lead ECGs, chemistry and hematology laboratory values, and AEs.

**Table 1:** Objectives and Endpoints (Continued)

#### 3. STUDY DESIGN

This is a Phase 2, multicenter, open-label study evaluating 2 INCB050465 treatment regimens based on the primary endpoint of ORR. Participants with relapsed or refractory FL (Grades 1, 2, or 3a) who have received at least 2 prior systemic therapies and who are ineligible for hematopoietic stem cell transplant will be screened for eligibility. A total of approximately 120 participants will be enrolled. The first 50 participants enrolled will be assigned at a 1:1 ratio to 2 study treatment regimens as follows (see Figure 1):

- Group A: INCB050465 20 mg QD for 8 weeks followed by 20 mg once weekly
- Group B: INCB050465 20 mg QD for 8 weeks followed by 2.5 mg QD

[figure not shown]
The remaining 70 participants will be allocated to 1 of the 2 treatment groups to better understand the safety and efficacy of that treatment regimen. The treatment group will be selected after evaluation of emerging safety and efficacy data from this and other monotherapy studies of INCB050465 in NHL, which are evaluating the same or similar dosing regimens, and will be implemented after the first 50 participants are enrolled. Participants allocated to the nonselected treatment regimen may switch to the selected treatment regimen or remain on their current treatment regimen, provided they have not met study-treatment withdrawal criteria, and there are no safety concerns for their current treatment regimen. There will be no rebaselining for participants who switch treatment regimens, and all participants will continue to follow the same assessment schedule.

Participants may receive treatment until disease progression, death, unacceptable toxicity, or consent withdrawal, whichever occurs first. Participants will be evaluated for ORR by an IRC and followed for CRR, DOR, PFS, OS, and safety.

An interim futility analysis is planned when the first 50 participants (Group A and Group B combined) have been evaluated for response or have permanently discontinued study treatment because of disease progression, withdrawal of consent, or death. The study will be terminated

for futility if  $\leq$  18 of the 50 participants have responded (ie, CR or PR) based on assessments provided by the IRC.

Figure 1: Study Design

<sup>a The first 50 subjects will be assigned at a 1:1 ratio to treatment Group A and treatment Group B. The remaining 70 subjects will be enrolled to the selected treatment Group (ie, either Group A or Group B).

#### 3.1. Randomization

Not applicable.

# 3.2. Control of Type I Error

There will not be any statistical comparison between the 2 treatment groups. Two-sided 95% CIs will be reported for all analyses when appropriate.

No adjustment for alpha-spending is considered as there are no plans to stop the study early for overwhelming efficacy. An IDMC will be assembled to monitor safety data and study conduct on a regular and ongoing basis during the study. The IDMC will also be charged with evaluating interim futility results. See Section 10 for details regarding interim analyses conducted in this study.

# **3.3.** Sample Size Considerations

Approximately 120 participants will be enrolled and assigned to either treatment Group A or Group B. The first 50 participants will be assigned at a 1:1 ratio to 2 treatment groups, and the remaining 70 participants will be allocated to the selected treatment group based on the emerging safety and efficacy data from this and other monotherapy studies of INCB050465 in NHL that are evaluating the same or similar dosing regimens. If the true ORR is 51% for participants in Group A and Group B, then with 120 total participants, there is approximately 93% probability of observing the lower bound of the 95% CI of ORR  $\geq$  35%.

bA futility analysis will be performed when the first 50 subjects have been evaluated for response.

#### 3.4. Schedule of Assessments

See Protocol Amendment 9 dated 23 DEC 2019 for a full description of all study procedures and assessment schedules for this study.

#### 4. DATA HANDLING DEFINITIONS AND CONVENTIONS

#### 4.1. Scheduled Study Evaluations and Study Periods

#### 4.1.1. Day 1

Day 1 is the date that the first dose of study drug (INCB050465) is administered to the participants.

#### **4.1.2. Study Day**

If a visit/reporting date is on or after Day 1, then the study day at the visit/reporting date will be calculated as

Day 
$$\# = (Visit/Reporting Date - Day 1 date + 1).$$

If the visit/reporting date is before Day 1, then the study day at the visit/reporting date will be calculated as

Day 
$$\# = (Visit/Reporting Date - Day 1 date).$$

A study day of -1 indicates 1 day before Day 1.

#### 4.1.3. Baseline Value

Baseline is the last nonmissing measurement obtained before the first administration of INCB050465, unless otherwise defined.

When scheduled assessments and unscheduled assessments occur on the same day and time of the assessment or time of first dose is not available, use the following convention to determine baseline:

- If both a scheduled and an unscheduled visit are available on the day of the first dose and the time is missing, use the scheduled assessment as baseline.
- If all scheduled assessments are missing on the day of the first dose and an unscheduled assessment is available, use the unscheduled assessment as baseline.

#### 4.1.4. Handling of Missing and Incomplete Data

In general, values for missing data will not be imputed unless methods for handling missing data are specified in this section or relevant sections. The original reported dates collected on the eCRF should be used in all relevant listings. The following rules will be used for handling missing or partial dates for analyses requiring dates.

When calculating time since initial diagnosis of cancer, partial diagnosis date will be handled in the calculation as follows:

- If only the day is missing, then the first day of the month will be used.
- If both the month and day are missing, then 01 JAN will be used.
- Otherwise, the time since diagnosis will not be calculated.

When the date of the last dose is used in deriving variables such as duration of treatment or TEAE flag, missing or partial date of last dose will be handled in the calculation as follows:

- If only the day is missing, then the earlier date of the last day of the month or the date that the participant discontinued treatment will be used.
- If both the month and day are missing, then the earlier date of 31 DEC of the year or the date that the participant discontinued treatment will be used.
- Otherwise, the date that the participant discontinued treatment will be used as the date of the last dose.

When calculating DOR, PFS, and OS, a partial date of death will be handled in the calculation as follows:

- If mmyyyy for the last known alive date = mmyyyy for the death date, then the day after the last known alive date will be used.
- If mmyyyy for the last known alive date < mmyyyy for the death date, then the first day of the death month will be used.
- Otherwise, the partial death date will not be handled.

When calculating time to onset or duration of a TEAE, a partial or missing AE onset/end date will be handled in the calculation as follows:

- If only the day is missing, then the first day of the month or Day 1, whichever is later, will be used as the onset date; the earlier date of the last day of the month or the date that the participant discontinued study or died will be used as the end date.
- If both the month and day are missing, then 01 JAN or Day 1, whichever is later, will be used as the onset date; the earlier date of 31 DEC or the date that the participant discontinued study or died will be used as the end date.
- Otherwise, Day 1 will be used as the onset date, and the missing end date will not be handled.

#### 4.2. Variable Definitions

#### 4.2.1. Body Mass Index

Body mass index will be calculated as follows:

BMI  $(kg/m^2) = [weight (kg)] / [height (m)]^2$ .

#### 4.2.2. Prior and Concomitant Medication

Prior medication is defined as any nonstudy medication started before the first dose of INCB050465.

Concomitant medication is defined as any nonstudy medication that is started accordingly:

- Before the date of first administration of INCB050465 and is ongoing throughout the study or ends on/after the date of first study drug administration.
- On/after the date of first administration of INCB050465 and is ongoing or ends during the course of study.

A prior medication could also be classified as "both prior and concomitant medication" if the end date is on or after first dose of INCB050465. In the listing, it will be indicated whether a medication is prior-only, concomitant-only, or both prior and concomitant.

For the purposes of analysis, all medications will be considered concomitant medications unless the medications can unequivocally be defined as not concomitant.

#### 5. STATISTICAL METHODOLOGY

## 5.1. General Methodology

Unless otherwise noted, SAS® software (SAS Institute Inc, Cary, NC; v9 or later) will be used for the generation of all tables, graphs, and statistical analyses. Descriptive summaries for continuous variables will include, but not be limited to, the number of observations, mean, standard deviation, median, minimum, and maximum. Descriptive summaries for categorical variables will include the number and percentage of participants in each category.

Interim analyses are planned for this study as defined in Section 10.

# **5.2.** Treatment Groups

This is a Phase 2, multicenter, open-label study. For the purpose of analysis, the 20 mg once weekly dosing period in Group A and the 2.5 mg QD dosing period in Group B are considered maintenance dosing periods. Data will be presented in summary tables by actual received treatment regimen and combined, with an exception for participants who cross over to the selected treatment regimen after the start of the maintenance dosing period. There will not be any statistical comparison between the treatment groups.

For participants who cross over from the initially assigned treatment regimen to the selected treatment regimen, if the crossover happens on/before the start of the maintenance period, then the participant will be summarized, according to the actual received treatment, in the selected treatment regimen; otherwise, the participant will be summarized in:

- A separate treatment regimen (ie, Crossover) for the safety summaries during the maintenance dosing period (eg. summaries of TEAEs and exposure).
- The initially assigned treatment regimen for all other summaries.

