#### 7.3.1. Best Overall Response and Overall Response Rate

For responses determined by the IRC, the best overall response for each participant will be provided by the Clinical Reviewer. A participant is considered an objective responder if they have a best overall response of CR or PR.

The ORR is the proportion of objective responders. Participants who do not have sufficient baseline or on-study response assessment information to be adequately assessed for response status will be included in the denominators in the calculation of ORR.

Best overall response as determined by the IRC will be descriptively summarized by treatment groups and combined. The ORR as determined by the IRC will be estimated with 95% CIs. Confidence intervals will be calculated based on the exact method for binomial distributions.

Because participants who switched to the selected treatment regimen after starting the maintenance dose received a mixture of the non-selected and selected maintenance regimens and could confound the efficacy evaluation of the non-selected treatment regimen, a sensitivity analysis of ORR as determined by IRC will be provided to summarize these crossover participants as a separate treatment regimen. In addition, the number of participants who achieved best overall response as determined by IRC after the time of crossover along with the best overall response data will be presented under this separate treatment regimen.

When applicable, sensitivity analysis of ORR as determined by the IRC may be provided excluding participants that do not have evaluable radiological images at baseline per the IRC.

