#### **Amendment 1 (26 AUG 2020)**

- Section 3 was modified to increase the target enrollment from approximately 100 to approximately 120 participants. This change is to align with recommendations from FDA.
- Section 4.1.4 was updated to include details of rules for handling partial/missing onset or end date of TEAEs in the calculation of time to onset or duration of a TEAE. Rules for partial/missing date of last dose were updated to include details for when both month and day are missing.
- Section 5.2 was modified to provide details regarding how crossover participants will be summarized.
- Section 5.3 was updated to add the all-screened population for the summary of analysis populations.
- Section 6.1.2 was updated to add relapsed/refractory status to the most recent prior therapy to the summary table of disease history because the response to last regimen before entering the study may be a prognostic factor for clinical outcomes.
- Section 6.2 was modified to add summaries of participants who are ongoing with treatment or still in the study.
- Section 6.4 was modified to change the calculations of duration of treatment and average dose during the maintenance dosing period because Group B with 2.5 mg QD was selected as the maintenance dose.
- Section 7.3 was updated to change the timing of the primary analysis to align with recommendations from FDA.
- Section 7.3.2 was modified to add "unknown" as a category for bone marrow involvement at baseline. Relapsed/refractory status to the most recent prior therapy was added to the subgroup analysis because the response to last regimen before entering the study may be a prognostic factor for clinical outcomes.
- Section 7.4.3 was modified to update references of censoring for PFS.

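### SAP 5.2 counts early switchers from Group A in the selected regimen from Day 1 but leaves lead-in failures in Group A, so by-regimen results are expected to tilt toward the selected regimen

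*SAP*

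**What the plan says.** The first 50 participants are assigned 1:1 and the remaining 70 go to the selected regimen (SAP 3 and 3.3). The SAP change log for Amendment 1 shows which regimen that was: "because Group B with 2.5 mg QD was selected as the maintenance dose". Participants on the other regimen may switch, "provided they have not met study-treatment withdrawal criteria, and there are no safety concerns for their current treatment regimen" (SAP 3). The first 8 weeks are the same in both groups. SAP 3 defines one as "Group A: INCB050465 20 mg QD for 8 weeks followed by 20 mg once weekly", and the other differs only in what follows the 8 weeks.

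SAP 5.2 sets the grouping rule: "Data will be presented in summary tables by actual received treatment regimen and combined". For switchers, "if the crossover happens on/before the start of the maintenance period, then the participant will be summarized, according to the actual received treatment", that is, in the selected regimen. Those who switch later form a separate Crossover group for maintenance-period safety and are otherwise kept in "The initially assigned treatment regimen for all other summaries". SAP 5.2 adds: "There will not be any statistical comparison between the treatment groups".

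Best overall response, DOR, PFS and OS are summarised by treatment group and combined (SAP 7.3.1, 7.4.2 to 7.4.4). Adverse events are tabulated by regimen, including separately for the initial daily-dosing period (SAP 9.2.3). The ORR crossover sensitivity analysis is introduced with "Because participants who switched to the selected treatment regimen after starting the maintenance dose received a mixture" (SAP 7.3.1). The CRR, DOR and PFS analyses in SAP 7.4.1 to 7.4.3 have the same scope: switches after maintenance has begun.

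**The concern.** The two regimens differ only from Day 57 (Protocol Table 4), but ORR, PFS and OS count everything from first dose. Take the Group A participants still in the lead-in when the selected regimen is put into effect. One who completes the lead-in and switches is counted in Group B from Day 1. One who has radiographic progression or unacceptable toxicity must stop treatment (Protocol 5.5.1), cannot switch, and remains in Group A. The same cohort on the same dose is thus divided partly by how it fared: successes can move and failures cannot.

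Response is the outcome most exposed. The first scheduled scan is at Week 8. In the earlier study, 7 of the 8 FL responses had occurred by the 9-week assessment (Protocol 1.3). Much of the response result is therefore settled before the regimens diverge. Lead-in adverse-event tables are also split by regimen although the treatment is the same. At stake is the descriptive account of each regimen, which is the stated reason for placing the last 70 participants in one group.

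**Working it through.** **The plan's own figures.** With n = 120, the smallest number of responders whose exact 95% lower bound is at least 35% is 53 (bound 35.1%). At a true ORR of 51%, P(X ≥ 53) = 94.4%. Also requiring more than 18 responders among the first 50 gives 93.1%, in line with the stated 93%. The futility probabilities reproduce as well: P(X ≤ 18 of 50) is 62.16% at 35% and 2.34% at 51%. All of these use combined data, so the grouping rule does not touch them.

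**Inputs from the documents.** As assigned, 25 in Group A and 95 in Group B (25 + 70). Planning ORR 51%. Lead-in 56 days. Accrual of 120 in about 1.0 year (Protocol 4.5).

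**Assumptions, because the documents give no figure.**
- The regimens are identical, with true ORR 51% in both.
- Selection takes effect at the 50th enrolment.
- A share q fails in the lead-in, with no responders among them.
- A share s of the remainder switches at the start of maintenance.

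**Group A participants in the lead-in at selection.** 120/365.25 × 56 = 18.4, half of them in Group A, so m ≈ 9.

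**Formulas.** Number moved: v = m(1 − q)s. ORR among those who complete the lead-in: 0.51/(1 − q).
- Displayed Group A ORR = [25 × 0.51 − v × 0.51/(1 − q)] / (25 − v)
- Displayed Group B ORR = [95 × 0.51 + v × 0.51/(1 − q)] / (95 + v)
- Displayed lead-in failure = 25q/(25 − v) in A and 95q/(95 + v) in B

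**Example: q = 10%, s = 1.** v = 9 × 0.9 = 8.1, and these carry 8.1 × 0.51/0.9 = 4.59 responders. Group A: (12.75 − 4.59)/16.9 = 48.3%. Group B: (48.45 + 4.59)/103.1 = 51.4%. Lead-in failure is shown as 2.5/16.9 = 14.8% against 9.5/103.1 = 9.2%, when it is 10% in both.

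**Results for m = 9, s = 1** (gaps from unrounded rates)

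| q | ORR A | ORR B | Gap (points) | Lead-in failure A | Lead-in failure B |
|---|---|---|---|---|---|
| 5% | 49.6% | 51.2% | 1.6 | 7.6% | 4.6% |
| 10% | 48.3% | 51.4% | 3.2 | 14.8% | 9.2% |
| 15% | 47.0% | 51.7% | 4.6 | 21.6% | 13.9% |
| 20% | 45.8% | 51.9% | 6.1 | 28.1% | 18.6% |

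With the unrounded m = 9.2, the 5% to 15% range is 1.7 to 4.8 points.

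**Sensitivity.**
- Half of those eligible switch (s = 0.5, m = 9): 0.7, 1.3 and 2.0 points at q = 5%, 10% and 15%.
- A 4-week delay in selection (m ≈ 4.6, s = 1): 0.7 points at q = 5% and 1.4 at 10%.
- Over m = 3 to 12, q = 5% to 20% and s = 0.5 to 1: 0.2 to 9.1 points, always toward Group B.
- No early switchers: zero.

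**As assigned.** With A = 25 and B = 95, the expected gap between identical regimens is zero in ORR and in lead-in failure.

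**The case against.** The strongest reply is that little rests on the by-regimen split. The SAP rules out any statistical comparison, and the sample-size statement and the futility rule use combined data. That stands, and it limits the importance of the point. It does not remove it, because the results are still displayed by regimen and will be read side by side.

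Further objections narrow the point:
- The rule covers switches on or before the start of maintenance. If a participant is reassigned mid-lead-in and fails afterwards, that failure moves too, which weakens the tilt. Failures before the switch still cannot move.
- SAP 5.2 has no explicit rule for someone who received neither maintenance dose. That such participants stay in Group A is the natural reading but an inference.
- The Week 8 scan has a window of ±1 week (Protocol Table 6), about Day 49 to Day 63, so a participant may switch on Day 57 before the scan is done or read. Progression at that scan does not always prevent a switch.
- High lead-in failure rates have little support. In the earlier study 12 of 63 stopped for adverse events, all but one of these events after the 9-week assessment (Protocol 1.3). One of the 11 evaluable FL participants had progression as best response without a complete postbaseline assessment. Rates of 20% or more are hard to defend from this.

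A reader might infer that early switchers bring 56 days of guaranteed event-free time into the Group B PFS curve. The documents do not support that as a material PFS advantage. There is no scheduled scan before about Day 49 in either group, so only deaths and unscheduled progression can differ before then, and eligibility requires a life expectancy of at least 12 weeks. The event-free time is real but runs only to the switch, and should matter little for medians or for rates from 6 months on.

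**Conclusion.** The mechanism holds. Under SAP 5.2, assignment to the selected regimen depends for some Group A participants on a post-baseline event that lead-in failure rules out, and the existing crossover analyses address only later switchers. By-regimen ORR, CRR, PFS, OS and lead-in safety are therefore expected to tilt toward Group B even if the regimens are identical.

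The size is uncertain and probably modest: about 1.6 to 4.6 ORR points for 5% to 15% lead-in failure under planned accrual, selection at the 50th enrolment and full switching. The distortion falls mainly on Group A. In the m = 9 scenarios Group B moves by less than one point, while Group A shrinks to about 17, where 8 of 17 has an exact 95% CI of 23% to 72%. The gap is small beside that imprecision.

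A reader might infer that the reported by-regimen results do favour the selected regimen, or that the primary result is biased. Neither follows. The tilt is an expectation and not a certainty in one dataset, the number of early switchers is not stated, and combined ORR and the futility decision are the same under any grouping.

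**What to change.** In SAP 5.2:
- State where participants who received no maintenance dose are counted, and report the number who switched on or before the start of maintenance.
- Present by-regimen ORR, CRR, DOR, PFS, OS and initial-daily-dosing-period safety by initially assigned regimen. This can be the main by-regimen display or, at the least, a sensitivity analysis beside the existing crossover analyses. It extends to early switchers the efficacy rule that already applies to late ones.
- Keep maintenance-period safety by regimen actually received. In overall-period safety tables, do not attribute an early switcher's maintenance-period events to the weekly regimen, which that participant never took.
- Add one supportive table by maintenance regimen actually started, among participants who start maintenance: PFS from first maintenance dose, and responses gained or deepened after Week 8.

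The cost is a few sentences in the SAP and one or two extra tables from data already collected. The downside is that a few early switchers who never took weekly dosing appear under Group A in the as-assigned efficacy display. The supportive table shows them by the maintenance they actually took.
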